### 5.3.4 Treatment Period – Cycle 1, Day 14 ( $\pm 3$ Days) (Cohort 1 only)

- Sparse PK blood sampling collected pre-dose
- Adverse event assessment using NCI CTCAE, Version 4.03, record AEs related to study procedures only (Cohorts 2 and 3 by telephone)
- Concomitant medications (Cohorts 2 and 3 by telephone)

### 5.3.5 Treatment Period – Cycle 2, Day 1

- Weight
- Physical examination
- Vital Signs
- ECOG Performance Status assessment
- Complete blood count with 5-part differential
- Serum biochemistry
- Sparse pharmacokinetic blood sampling taken pre-dose and at 1 hour and 2 hours ( $\pm 15$  min) post-dose
- Dispense poziotinib
- Adverse event assessment using NCI CTCAE, Version 4.03, record AEs related to study procedures only
- Patient Diary Collection
- Concomitant medications

### 5.3.6 Treatment Period – Cycle 2, Day 8 ( $\pm 1$ Day)

- Complete blood count with 5-part differential and platelets
- Adverse event assessment using NCI CTCAE, Version 4.03, record AEs related to study procedures only
- Patient Diary Collection
- Concomitant medications

### 5.3.7 Treatment Period – Cycle 3+, Day 1 (up to 24 months)

- Height and weight
- Physical examination
- Vital Signs

- ECOG Assessment
- Tumor assessment (to be performed after **Cycle 2**, and approximately every 6 weeks thereafter)
- Serum biochemistry
- Echocardiogram or MUGA scan to evaluate cardiac ejection fraction (3 months after the first treatment and then every 6 months thereafter, during treatment)
- Sparse pharmacokinetic blood sampling taken pre-dose and at 1 hour and 2 hours ( $\pm 15$  min) post-dose (**Cycle 3** only)
- Dispense poziotinib
- Adverse event assessment using NCI CTCAE, Version 4.03, record AEs related to study procedures only
- Patient Diary Collection
- Concomitant medications

### 5.3.8 End-of-Treatment Visit (35 $\pm$ 5] Days Post-Study Treatment)

The **End-of-Treatment Visit** is required 35 ( $\pm 5$ ) days after the last dose of poziotinib is administered. The following assessments are to be performed at this visit:

- Physical examination
- Vital signs
- ECOG Performance Status assessment
- Tumor assessment (unless the patient has documented disease progression or has undergone a tumor assessment within the previous 6 weeks)
- CBC with 5-part differential and platelets
- Serum biochemistry
- Echocardiogram or MUGA scan to evaluate cardiac ejection fraction
- Adverse event assessment
- Patient Diary Collection
- Concomitant medications

## 5.4 Description of Study Assessment Parameters

### 5.4.1 Relevant Medical History

At **Screening**, the patient's relevant medical history will be collected, to include the history of breast cancer, documentation of HER2 genetic confirmation, previous therapy, as well as significant and relevant past diseases and current medications.

### 5.4.2 Physical Examination

A complete physical examination, including a description of external signs of the neoplastic disease and co-morbidities, will be performed at **Screening** and **Day 1** of each cycle, and at the **End-of-Treatment Visit**. Symptom-directed examinations are required at other visits. Physical examinations are to be completed by a physician or other health professional licensed to perform

such examinations. Findings will be documented in the patient's medical record and on the appropriate CRF pages. Any abnormalities are to be recorded on the AE CRF.

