## 7.2 Adverse Events

An AE is defined as any untoward medical occurrence in a patient or clinical investigation patient, temporally associated with the use of a medicinal product, whether or not considered related to the medicinal product. Therefore, an AE can be any unfavorable and unintended sign (including an abnormal laboratory finding), symptom, or disease (new or exacerbated) temporally associated with the use of a medicinal product. A treatment-emergent AE (TEAE) is any AE that occurs from the first dose of study treatment until 35 ( $\pm 5$ ) days after the last dose of study treatment.

The study will record all AEs according to the information in [Section 7.3](#).

Examples of AEs **include**:

- Exacerbation of a chronic or intermittent pre-existing condition including either an increase in frequency and/or intensity of the condition.
- New conditions detected or diagnosed after investigational product administration.
- Signs, symptoms, or the clinical sequelae of a suspected drug interaction.
- Signs, symptoms, or the clinical sequelae of a suspected overdose of either investigational product or a concurrent medication.
- AEs may include pre-treatment or post-treatment events that occur as a result of protocol-mandated procedures, ie, invasive procedures.

Abnormal laboratory results are to be recorded as AEs, if any of the following conditions are met:

- The abnormal laboratory value leads to a therapeutic intervention.
- The abnormal laboratory value is considered to be clinically significant by the Investigator.
- The abnormal laboratory value is predefined as an AE in the protocol or in another document communicated to the Investigator by Spectrum or designee.

Examples of events that **do not** constitute AEs include:

- Medical or surgical procedures (eg, endoscopy, appendectomy); the condition that leads to the procedure is an AE.
- Situations where an untoward medical occurrence does not occur (eg, social and/or convenience admission to a hospital).
- Anticipated day-to-day fluctuations of pre-existing disease(s) or condition(s) present or detected at the start of the study that do not worsen.
- Planned and prescheduled hospitalizations and procedures.
- Progressive disease.

The adverse events of special interest identified with poziotinib treatment in this study include diarrhea, skin rash, oral cavity mucositis/stomatitis, fatigue, and vomiting/nausea.

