#### 7.3.1 Recording of Adverse Events

All AEs that occur from the first dose of study treatment through 35 ( $\pm$ 5) days after the last dose of study treatment is administered are to be recorded on the AE CRF. From the time the study Informed Consent is signed through the first dose of study drug administration, only SAEs that are related to study procedures are to be recorded.

The resolution of all AEs must be recorded at the end of the study. The following conventions will be followed when patient completes or discontinues from the study:

- If a patient dies, the date of death should be the date of AE stop for all ongoing AEs at the time of death.
- If a patient discontinues due to an AE(s), the outcome of the AE is to be followed for 35 ( $\pm$ 5) days from the date of discontinuation or until the AE has returned to Grade  $\leq$ 1. The status of the AE and the date of last contact with the patient will be captured. If the AE has not returned to Grade  $\leq$ 1 by the end of the study, the AE stop date should be left as ongoing.

All AEs will be classified by intensity/severity (**Section 7.3.2**), relationship to study drug (**Section 7.5**), and as serious or nonserious (**Section 7.7**) by the Investigator.

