#### **5.4.2.2 Treatment Emergent Adverse Events**

TEAEs are AEs that occur from the first dose of study treatment until 35 ( $\pm 5$ ) days after the last dose of study treatment. If it cannot be determined whether an AE is treatment-emergent (based on start date or, if the start date is missing then based on the stop date), then the AE will be considered treatment-emergent.

Summary of TEAEs by MedDRA SOC and PT will be presented in a separate table with any grade and with Grade 3 or 4. Patients who experience more than one type of AE will be counted under each of the corresponding PTs. Patients who experience different episodes of the same AE will be counted only once under the corresponding PT. Similarly, for determination of MedDRA SOC incidences, patients who experience multiple AEs under the same SOC will be counted only once for that SOC. Listing of all TEAEs will also be provided.

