#### **5.4.2.3 Treatment-Related Adverse Events**

Assessment of relatedness to study drug for all AEs will be classified by investigators and reported. "Definitely related", "probably related" and "possibly related" AEs will be considered as treatment related. An AE will be assigned as treatment-related if the relationship to study drug is missing.

The incidences of treatment-related AEs will be presented by MedDRA SOC and PT with any grade and with Grade 3 or 4.

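### Protocol 5.4.2 sends every examination abnormality to the AE form, contradicting 7.2 and 7.3.1, and the SAP's date-only TEAE definition can then count some stable baseline findings as treatment-emergent

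*Protocol*

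**What the plan says.** Protocol 5.4.2 requires a complete examination at Screening, on Day 1 of each cycle and at the End-of-Treatment Visit, "including a description of external signs of the neoplastic disease and co-morbidities". Findings go into the medical record and the relevant CRF pages, and then: "Any abnormalities are to be recorded on the AE CRF".

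Three other parts of the protocol govern the same entries:

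- **7.2** defines an AE as an unfavorable sign, "symptom, or disease (new or exacerbated) temporally associated with the use of a medicinal product". Its list of non-AEs contains progressive disease and "Anticipated day-to-day fluctuations of pre-existing disease(s) or condition(s) present or detected at the start of the study that do not worsen".
- **7.3.1** says that between consent and first dose "only SAEs that are related to study procedures are to be recorded".
- **5.3.2 to 5.3.7**, the on-treatment visit lists, tell sites to record only AEs that are related to study procedures.

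On the analysis side, Protocol 8.6 tabulates new-onset TEAEs and puts pre-treatment events in a listing. SAP 5.4.2.2 defines a TEAE by occurrence between first dose and 35 (±5) days after the last dose, without the new-onset wording. If timing cannot be determined from the start date or, failing that, the stop date, "then the AE will be considered treatment-emergent". SAP 5.4.2.3 adds: "An AE will be assigned as treatment-related if the relationship to study drug is missing".

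**The concern.** The 5.4.2 examination is meant to describe tumor signs and co-morbidities, in patients who all have metastatic disease and at least two earlier HER2-directed regimens. Abnormal findings at baseline are to be expected. At Screening a site cannot follow both 5.4.2 and 7.3.1. After first dose, it cannot follow both 5.4.2 and 7.2 for a stable palpable mass or a residual skin change. The gap looks unintended: 7.2 admits laboratory abnormalities only if they lead to intervention, are clinically significant or are predefined, while examination findings have no such filter.

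What is at stake is whether the AE tables describe what happened on poziotinib or partly describe the patients' condition at entry. Choosing the dosing schedule is a primary objective, and safety is reported by cohort without randomization, so term-level rates will be read closely.

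**Working it through.** No figure in the plan depends on this sentence, so there is none to reproduce. The check is to follow a stable baseline finding through the rules, then to size the effect.

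**Step 1. Which entries become TEAEs under SAP 5.4.2.2?**

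| How the finding is entered on the AE form | Result |
|---|---|
| At Screening, pre-dose start date | Not a TEAE |
| After first dose, with its true pre-dose start date | Not a TEAE |
| No start date, stop date before first dose | Not a TEAE |
| At Cycle 1 Day 1, visit date given as onset | Can be counted: examination and first dose fall on the same day (Protocol 5.3.2), and the AE listing in SAP 5.4.2 carries dates but mentions no time |
| At a later visit, visit date given as onset | TEAE |
| No start date, ongoing or stopped after first dose | Timing undetermined, so TEAE by default (SAP 5.1.2 rules out imputation) |

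The last three rows are the exposure. None of them meets a new-or-worsened test in the SAP, because it contains none. If causality is also blank, SAP 5.4.2.3 makes the event related.

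**Step 2. Size per patient.** SAP 3 gives 33 enrolled in Cohort 1 and 34 in Cohort 2; Protocol 8.1 gives 32 treated in Cohort 1. The shift in a preferred-term rate is k/N for k misclassified patients who would otherwise not have had the term:

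- k = 1: 1/32 = 3.1, 1/33 = 3.0, 1/34 = 2.9 percentage points
- k = 5: 5/32 = 15.6, 5/33 = 15.2, 5/34 = 14.7 percentage points

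The documents give no basis for k. The range 1 to 5 is an assumption, giving roughly 3 to 15 points. Repeated entries do not add up: 24 months is about 730/21 = 34.8 cycles, but SAP 5.4.2.2 counts a patient once per preferred term.

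**Step 3. Which outputs can move?**

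- *Overall TEAE incidence* (a primary safety measure, Protocol 8.6): earlier studies in Protocol Table 1 show any AE in 55/55, 20/20 and 39/39. Pooled, this is 114/114, with exact 95% lower limit 0.025^(1/114) = 96.8%. There is almost no room to rise.
- *Discontinuation because of a TEAE* (the other primary safety measure): a stable sign would not normally cause it.
- *Cohort stopping rule* (Protocol 3.1): needs Grade 3 or greater diarrhea, rash or stomatitis. SAP 3 reports that Cohort 2 continued after both reviews.
- *Preferred-term and treatment-related rates*, mainly low grade: exposed, by the amounts in Step 2.
- *Study day of first rash or stomatitis* (SAP 5.4.2.7, median and range): exposed for skin or oral findings coded to those groups. If study day 1 is the first-dose date, which the SAP does not state, one baseline finding dated Cycle 1 Day 1 sets the lower end of the range to Day 1.

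**The case against.** The strongest reply is that 5.4.2 is one loosely worded sentence among several safeguards. Protocol 5.4.1 collects breast cancer history and significant past disease at Screening. The sentence before the disputed one sends findings to the appropriate CRF pages. Protocol 7.3 refers sites to CRF completion guidelines, which are not among the documents and may settle the matter. Protocol 8.6 speaks of new-onset TEAEs. Protocol 7.5 requires a causality assessment for every AE, so the missing-data defaults are conservative backstops. Nothing shows that any site misrecorded a finding.

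Much of this stands. A reader might infer that stable tumor signs automatically become TEAEs and inflate the safety rates. The documents do not support that: a finding entered at Screening, or later with its true start date, stays out of the tables. Nor do they support a definite upward bias, because the on-treatment visit lists push toward under-recording. A reader might also expect the cohorts to be affected differently, since only Cohort 2 enrolled under Amendment 2, which shortened the washout and lifted the limit on earlier regimens. Residual baseline findings could differ, but nothing indicates that recording did. Finally, a breast mass or skin metastasis would not reach the grouped rash term; only findings coded to a rash-related term would.

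The safeguards do not remove the contradiction. They also do not close the gap in the SAP, because the new-onset wording stands in Protocol 8.6 and not in the definition that SAP 5.4.2.2 tells programmers to apply.

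**Conclusion.** The instruction in Protocol 5.4.2 contradicts 7.2 and 7.3.1, and under the SAP as written some stable baseline findings can be counted as TEAEs. This needs a particular kind of entry: no determinable date, or an onset given as the Cycle 1 Day 1 or a later visit date. Counting as related further needs a missing causality.

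The effect is about 3 percentage points per misclassified patient on a cohort's preferred-term rate, and about 3 to 15 points if 1 to 5 patients are affected. That number is an assumption. The exposure lies mainly in low-grade term rates, treatment-related rates and first-incidence day for skin or oral findings. The two primary safety measures and the stopping rule are little affected. The net direction of bias cannot be established from the documents. This is a documentation and definition fault worth correcting, not evidence that the reported safety rates are inflated.

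**What to change.** 1. Reconcile Protocol 5.3.1 to 5.3.7, 5.4.2, 7.2 and 7.3.1 together. Examination findings before first dose go to medical history or baseline pages. After first dose, only findings that are new or worsened from baseline and meet 7.2 go on the AE CRF. The visit lists should state the same recording rule as 7.3.1.
2. In SAP 5.4.2.2, define a TEAE as an event with onset, or worsening from baseline, within the window.
3. If the database is still open, query AE records that match a medical-history or screening finding without a grade increase, and ask for the true onset date.

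The SAP was approved in 2021 and describes enrollment in the past tense, so rewriting the protocol cannot change data already collected; items 2 and 3 are the ones that can still affect the tables. The cost is a few sentences of text and the query work. No clinical rule changes.

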### 5.4.3 Vital Signs

Vital signs, to include temperature, blood pressure, heart rate, and respiratory rate, are to be recorded at **Screening** and **Day 1** of each cycle and at the **End-of-Treatment Visit**. Heart rate and blood pressure will be recorded before poziotinib administration.

### 5.4.4 ECOG Performance Status

Patients' Performance Status will be evaluated using criteria as developed by the Eastern Cooperative Oncology Group ([Appendix 2](#)) at **Screening** and **Day 1** of each cycle and at the **End-of-Treatment Visit**.

### 5.4.5 Clinical Laboratory Tests

A local laboratory will be used to process all clinical specimens. The following clinical laboratory parameters will be evaluated in this study:

- **Complete Blood Count (CBC):** A CBC, including white blood cells (WBC), with 5-part differential, hemoglobin, and platelets will be performed at **Screening, Day 1** and **Day 8** of **Cycle 1** and **Cycle 2, Day 1** of subsequent cycles, and at the **End-of-Treatment Visit**. The results of the laboratory assessments should be evaluated and medically accepted by the responsible physician before the start of each cycle.
- **Prothrombin Time (PT) and International Normalized Ratio (INR):** Only for patients with active bleeding disorders or use warfarin or other coumadin-derived anticoagulants a PT/INR need to be evaluated at **Screening**.  
Use of warfarin or other coumadin-derived anticoagulants should be avoided during treatment with poziotinib. When it cannot be avoided, regular monitoring of INR is required and prior authorization from study medical monitor is required.
- **Chemistry Panel:** A comprehensive chemistry and electrolytes, including blood urea nitrogen (BUN), AST/SGOT, ALT/SGPT, alkaline phosphatase (ALP), GGT (only at screening), total bilirubin, albumin, calcium, lactate dehydrogenase, sodium, potassium, chloride, phosphate, magnesium, creatinine, uric acid, and glucose, will be performed at **Screening, Day 1** of each cycle, and at the **End-of-Treatment Visit**.
  - **Special note for the Day 1 sampling of each cycle:** If possible, blood samples should be drawn on **Day 1** of each cycle (prior to treatment); however, for logistical reasons, it is also acceptable to draw samples for assessment up to 7 days prior to the start of a cycle. The results of the laboratory assessments should be evaluated and medically accepted by the responsible physician before the start of each cycle.
- **Pregnancy Test:** A urine  $\beta$ -hCG test will be performed at **Screening** for all women of childbearing potential.

#### 5.4.6 Pharmacokinetics

All patients will have blood samples drawn pre-dose and at 1 hour and 2 hours ( $\pm 15$  min) post-dose for sparse PK sampling on **Day 1** of **Cycles 1, 2, and 3** and pre-dose on **Day 14** ( $\pm 3$  days) of **Cycle 1 (Cohort 1 only)**.

If consented, intensive PK samples will be drawn pre-dose and 30 minutes, 1, 1.5, 2, 3, 4, 6, and 24 hours post-dose on **Day 1** of **Cycle 1**. In addition, if a patient presents with a potentially drug-related SAE at any time during the study, PK samples may be collected during the clinic visit for PK analysis.

#### 5.4.7 Cardiac Ejection Fraction

Cardiac ejection fraction will be assessed by either echocardiogram or multi-gated acquisition (MUGA) scan at **Screening**, 3 months after first treatment, then every 6 months thereafter, while the patient is being treated, and at the **End-of-Treatment Visit**.

#### 5.4.8 Tumor Assessment

Tumor assessment must be performed by Investigators using computed tomography (CT) or magnetic resonance imaging (MRI) at **Screening** up to 30 days prior to **Cycle 1, Day 1**. Imaging studies performed prior to the signing of Informed Consent as part of the site's routine standard of practice are allowed at the discretion of the Sponsor. This information is to be discussed with the Medical Monitor before the patient is enrolled in the study.

Tumor assessments will be performed every 6 weeks ( $\pm 14$  days) until disease progression, death, intolerable adverse events, or for up to 24 months.

Each subsequent tumor assessments must use the same Baseline radiologic technique, either CT or MRI. Tumor assessments will be made according to RECIST criteria, Version 1.1 [23] using appropriate radiologic imaging or other techniques. For radiographic assessment, CT or MRI must be performed at every assessment.

Measurable and non-measurable lesions that will not be followed by radiological methods should be documented appropriately.

#### 5.4.9 Confirmation of Diagnosis of HER2-Positive Breast Cancer

Confirmation of HER2 overexpression or gene-amplified tumor via immunohistochemistry (IHC) with IHC 3+ or IHC 2+ with confirmatory fluorescence *in situ* hybridization (FISH) is required.

#### 5.4.10 Concomitant Medications

All medications administered from **Screening** to the **End-of-Study Visit** will be recorded on the CRF. A concomitant medication is any medication a patient is using from **Day 1** of **Cycle 1** to the **End-of-Study Visit**. The study drugs are not considered concomitant medications.

All concomitant medications recorded at study entry must have a related, ongoing concomitant illness listed under the medical history at the time of patient entry into the trial unless the medication is used for prophylaxis. Patients may continue to use any ongoing medications not prohibited by the protocol.

All prescription and over-the-counter medications at trial entry as well as any new medications started during the trial must be documented on the CRF and in the source documents. The documentation should continue until 35 ( $\pm$ 5) days after the last dose of study drug.

Premedications (such as antiemetics) used for supportive care are allowed as per institutional standards or guidelines.

Endocrine or hormonal therapy for hormonal receptor positive breast cancer is allowed.

Other supportive and palliative therapies may be allowed during the study upon prior authorization from study medical monitor.

#### **5.4.10.1 Premedication and Supportive Treatment**

All patients will receive prophylaxis with loperamide. Loperamide will be supplied by Sponsor and is to be taken by all patients on the following schedule:

- **Days 1 to 56:** 4 mg two times a day (bid), or three times a day (tid) if needed
- **Days 56 until end of treatment:** 4 mg taken as needed, but not to exceed 16 mg/24 hours

Patients should also receive prophylactic mouth care to prevent possible mucositis and or stomatitis during poziotinib treatment.

Mucositis/stomatitis should be treated in a supportive manner aiming to control symptoms. Prophylactic methods to reduce or prevent mucositis/stomatitis include:

- Avoidance of spicy, acidic, or irritating foods and alcoholic drinks
- Use of solutions such as saline (diluted solution with salt water and baking soda by dissolving ½ teaspoon of salt and 1 teaspoon of baking soda in approximately 1 liter of water) and using this solution every 4 hours
- Use of Nystatin solution
- Use of Magic Mouthwash (for instance, combination of viscous lidocaine 2% + Mylanta + diphenhydramine elixir + prednisolone solution)

Pre-medications (including, but not limited to antiemetics), as per Institutional standard of care, should be administered before poziotinib on **Day 1**.

